## Background

Opioid requirements in hospitalized patients varies at least ten-fold depending on a host of factors, many of which are unknown to clinicians or poorly characterized in medical records. Important factors include genetic sensitivity, alcohol consumption, previous opioid use, pain intensity etc. Even within specific categories, say chronic opioid users, there is tremendous variation in sensitivity — and thus opioid requirement under various conditions.

In most situations, patients can simply be queried about pain, and their responses used to guide analgesic administration. But during anesthesia, patients do not experience pain (a conscious response). But patients nonetheless clearly experience and respond to nociception even during general anesthesia. Increases in blood pressure and heart rate roughly indicate when patients are experiencing nociceptive stress, but neither is reliable. No other routine anesthetic monitors provide useful indications of nociceptive intensity.

Even experienced anesthesiologists cannot reliably predict or estimate opioid requirements in individual patients. Consequently, most routinely give small amounts of opioid during general anesthesia, and often give a bolus of a slow-onset, long-acting opioid such as morphine or hydromorphone at the end of surgery to provide analgesia during the initial hours of post-anesthetic recovery. The doses given, while reasonable *on average*, often prove inadequate or excessive for individual patients. Those given too much awaken slowly at the end of anesthesia and may breathe poorly; those given inadequate doses suffer intense pain upon awaking and it often takes many boluses of opioid and considerable time to control their pain.

There are now several devices that estimate nociception during general anesthesia including the Surgical Pleth Index, pupillary reflexes, galvanic skin responses, and heart-rate variability. The best-validated system is the PMD-200 system from Medasense (Ramat Gan, Israel). It is comprised of a console and designated finger probe and a single-use sensor. The PMD-200 acquires 4 signals: photoplethysmography, galvanic skin response, accelerometry, and skin temperature. Based on a random forest analysis, the device generates the NOL index. The intended use of NOL is to assess nociception input during general anesthesia.

NOL is a unitless index that extends from 0 to 100, with values exceeding 25 indicating that patients are experiencing substantial nociceptive input. Previous work in anesthetized patients has shown that NOL values are low in the absence of nociceptive input (e.g., when unstimulated) and progressively increase in response to progressively more intense stimuli (e.g., tetanic electrical stimulation, skin incision, and intubation). At

this point, there are only limited data — largely unpublished — showing that titrating intraoperative opioids to NOL improves post-anesthetic recovery.

Most studies of NOL titration and recovery characteristics were conducted with remifentanil infusions, using target-controlled infusion, an opioid-dosing technique that is rarely used in the United States and not approved by the Food and Drug Administration. Whether intraoperative titration will improve recovery characteristics will depend critically on the choice of opioid(s). Remifentanil is easy to titrate because the drug is potent and ultra-short acting. Patients given remifentanil are thus usually given a bolus of long-acting opioid such as morphine or hydromorphone near the end of surgery to bridge the analgesic gap between remifentanil discontinuation and arrival in the PACU. Thus, PACU recovery characteristics are largely determined by the long-acting opioid bolus timing and dosage which is given empirically and independent of NOL guidance.

Fentanyl is probably the ideal intraoperative anesthetic for NOL testing because of its intermediate and context-sensitive half-life (effect is proportional to not just dose but duration of administration). Fentanyl is initially short acting (typically 15 minutes) and thus easy to titrate. Its action is not terminated by metabolism; instead, the lipophilic drug redistributes into fat tissue. But after several hours of administration, much of the fat reservoir fills, and the drug's effect then becomes constrained by rate of metabolism, and can exceed the duration of morphine effect. Fentanyl is thus initially short acting, when titration is necessary, but then becomes long-acting and remains effective at least during the initial part of recovery. Patients who have long operations ( $\geq 2$  hours) who are given the “right amount” of intraoperative fentanyl have effective pain control without use of a long acting opioid.

## Specific Aims

Previous work has shown that NOL (Medasense, Ramat Gan, Israel) accurately quantifies nociception during general anesthesia. Presumably, titrating opioids to NOL will therefore provide individual guidance so that patients will be given about the right amount. Patient given the right amount will presumably awaken quickly when anesthesia is done, and have good initial pain control in the PACU. To the extent that NOL titration facilitates optimal opioid dosing, patients are likely to have better PACU experiences — which would be an important outcome that clinicians and regulators are likely to take seriously.

### ***Aim of this study:***

Demonstrate that **intraoperative NOL-guided titration of fentanyl improves initial recovery characteristics**. All times below are relative to when sevoflurane anesthesia is discontinued.

**Primary hypothesis.** Pain scores (0-10 verbal response scale) at 10-minute intervals during the initial 60 minutes of recovery are less in patient with NOL-guided fentanyl than with routine care, with 1 point being considered a clinically meaningful difference

**Primary Outcome.** Pain Scores at 10-minute intervals during the initial 60 minutes of recovery

**Secondary hypothesis.** NOL patients are more likely to have a “good” pain scores, defined as < 5 (i.e., 0,1,2,3 or 4) across the measured intervals, with a relative 10% or more increase in the proportion of good scores being considered clinical meaningful.

**Secondary Outcome.** Whether or not the pain score at any measured interval is < 5.

We will also consider several exploratory hypotheses.

**Exploratory hypothesis 1.** Fewer analgesic rescue boluses are required in NOL-titrated patients during the initial 60 minutes of recovery.

**Exploratory hypothesis 2.** NOL-guided patients are no less alert (Ramsay score) during the initial 60 minutes of recovery than those given fentanyl per routine, based on a clinically meaningful non-inferiority delta of 20%.

**Exploratory hypothesis 3.** Emergence from anesthesia (discontinuation of sevoflurane anesthesia to extubation) is faster in NOL-guided patients.

**Exploratory hypothesis 4.** Fewer NOL-guided patients experience post-operative nausea and/or vomiting (PONV) **at least once** during the initial 60 minutes of recovery.

**Exploratory hypothesis 5.** There are fewer episodes of inadequate analgesia (too much or too little) in NOL-guided patients. Inadequate analgesia will be defined by systolic pressure  $\geq 140$  mmHg, heart rate exceeding 90 beats/min, diaphoresis, tearing, or movement. Excessive anesthesia will be defined by MAP  $< 65$  mmHg or BIS  $< 40$ . All values must return to normal for at least 15 minutes for a subsequent deviation to be

considered a new episode. The outcome for a patient will be the number of episodes.

**Exploratory hypothesis 6.** There will be less respiratory depression during the initial 60 minutes of recovery, defined as respiratory rate <8 breaths/min or saturation <90% for at least 1 minute while on nasal cannula oxygen at 2 L/min; unplanned airway support after PACU admission (nasal trumpet, oral airway, PPV, BiPap, or intubation with a laryngeal airway or endotracheal tube); or naloxone use.

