## **Protocol**

Patients will be premedicated with 0-2 mg midazolam per preference of the attending anesthesiologist. General anesthesia will be induced as preferred by the attending anesthesiologist, usually with a combination of lidocaine 1 mg/kg, propofol 1-4 mg/kg, fentanyl 1-2 µg/kg, and rocuronium 0.6-1.2 mg/kg or succinylcholine 1.5 mg/kg, as clinically appropriate. The trachea will be intubated and the lungs will be mechanically ventilated per clinical routine. General anesthesia will be maintained with sevoflurane at a target concentration of 0.7 %, with the dose being adjusted based on apparent clinical need, supplemented with fentanyl. Sevoflurane will be given per clinical routine and adjusted as usual in response to vital signs, surgical need, etc. Nitrous oxide will not be used for induction or during anesthetic maintenance. Vasopressors, antihypertensives, and drugs to control heart rate may be given as clinically indicated. Depth of anesthesia will be recorded for all patients using BIS.

Unless another opioid is clinically indicated, fentanyl will be the only opioid used for induction and throughout anesthesia. Long-acting opioids such as morphine will not be given. No opioid will be given unless clinically indicated from the end of surgery until patients reach the recovery unit.

Patients will be randomized 1:1, stratified for pre-operative chronic opioid use, with random-sized blocking to NOL guided analgesic management or routine care. The randomization table will be prepared by trial statisticians, and allocation will be concealed until shortly before anesthetic induction with a web-based randomization system.

- 1) **Routine opioid management.** Clinicians will be blinded to NOL monitoring and use clinical judgement to determine how much fentanyl should be given, and when. Clinical judgement will be according to their standard practice and may include interpretation of blood pressure, heart rate, diaphoresis, tearing, and pupil size. Boluses of fentanyl 1 µg/kg actual body weight (ABW), up to a maximum dose of 100 µg per bolus, can be given per clinical judgement.  
**Towards the end of the surgery (approximately 30-45 minutes before end of surgery, based on clinical judgment), the boluses of fentanyl will be reduced to 0.5 µg/kg ABW, up to a maximum of 50 µg per boluses. Boluses will be given per clinical judgment.**

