## ***Data Analysis***

Randomized groups will be assessed for balance on baseline characteristics using the standardized differences, defined as the difference in means or proportions divided by the pooled standard deviation. An absolute standardized differences  $> 0.10$  will be considered as imbalanced. We will use modified intent-to-treat such that all randomized patients receiving any of the study intervention (either one, even if the incorrect treatment was applied) will be included in the primary analyses.

**Primary outcome.** We will assess the treatment effect of NOL guided analgesic management versus routine care on mean pain score with the first 60 minutes of the recovery period using a linear mixed effects model adjusting for within-patient correlation across the 7 time points, and fixed effects for intervention, time (as categorical) and the stratification variable of pre-operative chronic opioid use. We will also assess the treatment-by-time interaction. We will decide on the most appropriate correlation structure empirically, using the AIC criterion, and considering either AR(1), exchangeable, or other correlation.

**Sensitivity analysis.** As a sensitivity analysis we will assess the treatment effect on pain score using a mixed effects proportional odds model in which we consider patient as a random effect while estimating the proportional odds ratio for patients having a better outcome on NOL than standard care, again adjusting for the stratification variable.

**Secondary outcome.** We will assess the treatment effect of NOL versus routine care on the proportion of patients with pain score less than 5 (i.e., 0-4) across the 7 time points using a generalized linear mixed effects model with a binary outcome ( $<5$  or  $\geq 5$ ), log link

(to be able to estimate relative risk), patient as random effect and modeling the within-subject serial correlation using an R matrix (considering autoregressive AR(1), exchangeable and unstructured correlation structures), with treatment group and the stratification variable as fixed effects. We will also assess the treatment-by-time interaction. Results will be reported as the relative risk (95% CI) of having a “good” pain score over time in NOL versus routine care.

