### **Sample size justification.**

**Pilot patients:** N=21 pilot patients were enrolled prior to the start of the study to familiarize the study team with the protocol and identify any systematic issues that might result in protocol modifications. In the below sample size calculations we used data on these patients to help estimate the standard deviation of the primary outcome (pain score) and the within-subject correlation on the pain score across the 7 measurement times.

**Required Sample Size.** We plan the study to have 90% power at the 0.05 significance level to detect a difference in mean pain score of 1.25 or more between groups when measured over 10 minutes intervals during the first 60 minutes in the recovery period and analyzed using a linear mixed effects regression model. Based on our pilot study data (N=21) and previous work (SOLAR study report, Figure 1) we estimate the standard deviation of the pain score to be about 2.5 and the within-subject correlation to be approximately 0.60 when assumed to be exchangeable across measurements. Making these assumptions we would need a total of 116 patients before accounting for interim analyses, and a maximum of 144 after adjusting for planned interim analyses at each 1/4 of the maximum sample size. We therefore plan to randomize and enroll a maximum of 144 patients under these assumptions.

**Interim analyses.** We will conduct interim analyses for efficacy and futility at each 1/4 of the maximum sample size using a group sequential design and conservative gamma spending function parameters of -2 for efficacy and 0 (more aggressive) for futility. If the alternative hypothesis effect size (1.25 point difference) is true in the population sampled from, with the planned sample size we will cross an efficacy or futility boundary at each of the 4 looks with respective cumulative probabilities of 0.16, 0.50, 0.78 and 1.0.

Z-statistic boundaries for efficacy (futility) will be  $> 2.80$  ( $\leq 0.156$ ),  $> 2.58$  ( $\leq 0.667$ ),  $> 2.34$  ( $\leq 1.42$ ), and  $> 2.09$  ( $\leq 2.09$ ). The average total sample size across many simulations, assuming the alternative hypothesis is true (a true difference of 1), is N=64.

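### Power of 90% applies to a 1.25-point difference, not to the plan's own meaningful difference of 1 point, where it is about 73–75%; the interim section also gives its alternative hypothesis two values

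*Combined protocol and SAP*

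**What the plan says.** Under Aim of this study, the primary hypothesis is that pain scores are lower with NOL guidance, "with 1 point being considered a clinically meaningful difference".

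Under Sample size justification, power is fixed at 90% and alpha at 0.05. The stated purpose is "to detect a difference in mean pain score of 1.25 or more between groups". This gives 116 patients without interim looks and a maximum of 144 with looks at each quarter. The Interim analyses paragraph names 1.25 as the alternative and prints Z bounds for efficacy of 2.80, 2.58, 2.34 and 2.09, and for futility of 0.156, 0.667, 1.42 and 2.09. The internal pilot reassessment at the second look also targets 1.25.

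The same Interim analyses paragraph ends with an average total sample size of 64, "assuming the alternative hypothesis is true (a true difference of 1". So one paragraph gives the alternative hypothesis as both 1.25 and 1.

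The plan does not say why it targets more than the meaningful difference, what the power is at 1 point, or whether the futility bounds are binding.

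**The concern.** The difference that matters clinically and the difference the trial is sized for are not the same, and the plan does not connect them. The stray alternative of 1 invites a reader to suppose that the operating characteristics were worked out at 1 point.

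What is at stake is how a negative result is read. Futility is tested at every interim look, with spending that the plan itself describes as the more aggressive. If the trial stops for futility or ends non-significant, the natural benchmark is the 1 point in the primary hypothesis. The error rates behind the bounds were set at 1.25, so that reading would claim more than the design supports. Human Subjects Protection says the results are meant to inform the design of a Phase 3 trial, so the wording of a negative result has consequences.

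**Working it through.** **Inputs.**
- SD: "we estimate the standard deviation of the pain score to be about 2.5" (Sample size justification).
- Correlation: "the within-subject correlation to be approximately 0.60 when assumed to be exchangeable across measurements" (same section).
- Seven readings: "adjusting for within-patient correlation across the 7 time points" (Data Analysis).
- Equal allocation: "Patients will be randomized 1:1, stratified for pre-operative chronic opioid use" (Protocol).
- Looks at 36, 72, 108 and 144 patients, with the bounds listed above.
- Assumptions, because the plan is silent: two-sided 0.05 and no dropout.

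**Variance of a patient's mean score.** 2.5² × (1 + 6 × 0.60)/7 = 6.25 × 4.6/7 = 4.107, so the SD is 2.027.

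**The plan's fixed sample size.** N = 4 × (1.960 + 1.282)² × 4.107/1.25² = 110.5, or 112 with equal whole arms. A t-based calculation gives 114; with six readings instead of seven it gives 116. The stated 116 is reproduced to within 3%.

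**Range used.** SE = √(4 × 4.107/N) gives the favourable end. The other end takes 116 as exact for 90% power, which implies an SD of 1.25 × √116/(2 × 3.242) = 2.077.

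**Operating characteristics.** These come from recursive integration over the printed bounds, confirmed by simulation, with the futility bounds followed:

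| True difference | Power | Futility at looks 1–3 | Total miss | Average N |
|---|---|---|---|---|
| 1.25 | 0.904 to 0.891 | 0.077 to 0.087 | 0.096 to 0.109 | 83.5 to 84.8 |
| 1.0 | 0.750 to 0.730 | 0.189 to 0.204 | 0.250 to 0.270 | 92.7 to 93.3 |

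The total miss is 1 minus power and contains the early futility stops. With the futility bounds ignored, power at 1.0 is 0.821 to 0.802.

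So 144 patients and the bounds fit 1.25. Holding 90% power at 1 point with the same four looks would need about 144 × 1.25² = 225 patients.

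**What a futility stop shows.** At look 3 the SE is √(4 × 4.107/108) = 0.390. The futility bound is an observed difference of 1.42 × 0.390 = 0.55. An unadjusted 95% interval there is 0.55 ± 1.96 × 0.390, or about −0.21 to 1.32, which contains 1 point. At that look, an interval excluding 1 point would need an observed difference below 1 − 0.764 = 0.24.

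**The average of 64.** The plan's own cumulative stopping probabilities at 1.25 (0.16, 0.50, 0.78, 1.0) imply 36 × (1 + 0.84 + 0.50 + 0.22) = 92. For a true 1.5 it prints 0.21, 0.62, 0.91 and 1.0, which imply 36 × (1 + 0.79 + 0.38 + 0.09) = 81, as printed. An average of 64 at a smaller effect, against 81 at 1.5, is also the wrong order for this design. The printed 0.16, 0.50 and 0.78 match efficacy crossing alone at 1.25 (0.160, 0.502, 0.780 with SD 2.077). For either boundary the figures are about 0.21–0.22, 0.57–0.59 and 0.87–0.88, which is why the recomputed average is 84–85 and not 92.

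**The case against.** The smallest difference that matters and the difference a trial is sized to detect are separate quantities, and choosing a larger target is a legitimate use of limited resources. The plan prints 1.25 beside its 90% and never claims 90% power at 1 point. It calls itself a pilot for a Phase 3 trial, and it nowhere says that a futility stop will be reported as excluding a meaningful benefit. All of this stands. The choice of 1.25 is not an error, and the only outright contradiction in the text is the alternative of 1 with its N of 64.

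A reader might infer that the trial misses any meaningful effect about one time in four. The figures do not support that: the rate applies at exactly 1 point, and power is already about 0.81–0.82 at 1.1 and 0.96–0.97 at 1.5. Nor are the one-in-four miss and the one-in-five early stop separate risks, since the second lies within the first.

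A reader might also object that the last look can succeed at an observed difference of about 0.71 points (2.09 × 0.338), below the meaningful 1. That is normal for a test against zero and is no defect.

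The objection does not supply the missing information: power at the one difference the plan calls meaningful, and the limit this puts on a negative conclusion.

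**Conclusion.** The point holds as a matter of disclosure and consistency, not as a fault in the sample size. The design does what it says at 1.25. At exactly 1 point, power is about 73–75%, against 89–90% at 1.25. This rests on SD 2.5, exchangeable correlation 0.60, seven readings, no dropout and futility bounds that are followed; if they are ignored, the miss rate at 1 point is 18–20% instead of 25–27%. A result at the look-3 futility bound remains compatible with a 1-point benefit, so neither a futility stop nor a non-significant test is enough to exclude one. The average N of 64 is wrong under either value of the alternative.

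**What to change.** Keep the 144 patients and the bounds, and change wording only.

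1. In Interim analyses, use one alternative, 1.25, throughout. Replace the average N of 64 with the recomputed value (about 84–85 at 1.25; about 93 at 1.0 if that is also reported). Take the stopping probabilities from the same run, labelled as efficacy alone or either boundary.
2. In Required Sample Size, state that 90% power applies to 1.25. Add that at the meaningful difference of 1 point power is about 73–75%, with a 19–20% probability of an early futility stop, provided the futility bounds are followed.
3. In Data Analysis, state that a futility stop or non-significant result will be reported as excluding a meaningful benefit only if the confidence interval, adjusted for the sequential design, excludes 1 point.

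The cost is a less favourable power statement and a more cautious negative conclusion. No patients are added.

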#### **Inclusion criteria**

- 1) Adults having major non-cardiac surgery expected to last  $\geq 2$  hours;
- 2) American Society of Anesthesiologists physical status 1-3;
- 3) Age 21-85 years old;
- 4) Planned endotracheal intubation.

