## **Measurements**

Demographic and morphometric characteristics will be recorded, including sex, age, race, height, weight and opioid use in the last month (estimated morphine equivalents). Anesthesia clinicians cannot be blinded since they will need to titrate opioid administration to NOL. However, all postoperative care and evaluations will be fully blinded to randomization, thus preventing measurement bias. There will thus be separate teams of investigators for the intraoperative and postoperative portions of the trial.

All routine anesthetic monitoring will be used, and the results recorded electronically. Blood pressure will be evaluated continuously with an arterial catheter if clinically indicated; otherwise, blood pressure will be evaluated oscillometrically at 3-

minute intervals. Anesthetic drugs including end-tidal sevoflurane concentration, type and duration of surgery will also be recorded electronically at one-minute intervals. Inadequate analgesia will be defined by systolic pressure  $\geq 140$  mmHg, heart rate exceeding 90 beats/min, MAP  $< 65$  mmHg. Vasoactive drugs and episodes and duration of hypotension (mean arterial pressure  $< 65$  mmHg, occurrences of MAP  $< 60$  & MAP  $< 55$ ) will be recorded. Muscle-relaxant administration will be recorded as well.

During surgical stimulation under general anesthesia, a NOL of zero indicates no nociceptive response, and NOL of 100 indicates extreme nociceptive response. NOL values below 25 represent nociception/anti-nociception balance, suggesting either no nociception in the absence of noxious stimuli, or effective analgesia in the presence of noxious stimuli. NOL values are recorded by the Medasense monitor at 5-second intervals.

The clock on the NOL monitor will be synchronized to that driving the electronic record. Nociception will be continuously evaluated in all participating patients. However, values will be blinded to clinicians when patients are assigned to the routine opioid management group.

We will record the time of reversal agent administration wrist, the time at which sevoflurane is discontinued, along with the end of surgery (last stitch), eye opening, and extubation. Discontinuation of sevoflurane will be considered the end of anesthesia and the beginning of recovery.

The following will be recorded on the PMD-200 monitor, using the EVENTS button, as accurately as possible:

1. Medications administration:
  - a. Fentanyl
  - b. Vasoactive drugs

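### Exploratory hypothesis 5 rests on a bare episode count that ignores duration and case length, so the count need not rise as intraoperative control worsens

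*Combined protocol and SAP*

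**What the plan says.** Exploratory hypothesis 5, under Aim of this study, states: "There are fewer episodes of inadequate analgesia (too much or too little) in NOL-guided patients". Two sets of criteria feed it. The inadequate side is systolic pressure of 140 mmHg or more, or "heart rate exceeding 90 beats/min, diaphoresis, tearing, or movement". For the other side the text reads "Excessive anesthesia will be defined by MAP" below 65 mmHg, or BIS below 40.

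The counting rule is that "All values must return to normal for at least 15 minutes for a subsequent deviation to be" treated as separate from the one before. The patient-level measure is then fixed in a single sentence: "The outcome for a patient will be the number of episodes". The normal interval is thus required of all criteria together, in both directions, and the patient's outcome is a single pooled count.

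No duration, severity or length of surgery enters that outcome. The Inclusion criteria set an expected minimum of 2 hours for surgery and no maximum. The Data Analysis section describes analyses for exploratory outcomes 1 to 3 only, so no analysis text for outcome 5 supplies a correction. The Measurements section plans to record episodes and duration of hypotension but does not connect this to hypothesis 5.

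**The concern.** Fewer episodes are to be read as better control. For that reading to be safe, the count should rise as control gets worse. Under a 15-minute all-normal rule it does so only up to a point. Once deviations come close together, clear 15-minute gaps become scarce and separate deviations merge into one long episode. Because every criterion must be normal at once, one persistently abnormal signal holds an episode open, and a swing from too deep to too light within 15 minutes is counted once although it contains both errors that the hypothesis names.

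Hypothesis 5 is the only listed hypothesis about intraoperative balance between too much and too little, which is the mechanism that Specific Aims presumes. If NOL guidance broke long abnormal stretches into short, separated ones, the count could fail to show the gain or could show it with the wrong sign.

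**Working it through.** The plan gives no rate, expected count or power for hypothesis 5, so there is no figure of its own to reproduce.

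**1. The rule alone (no assumed rates).** Take 180 minutes and 3-minute deviations at fixed spacing. A deviation is new only if at least 15 clear minutes precede it.

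| Pattern | Minutes abnormal | Episodes |
|---|---|---|
| Every 60 min | 3 × 3 = 9 | 3 |
| Every 18 min (gap 15) | 10 × 3 = 30 | 10 |
| Every 17 min (gap 14) | 11 × 3 = 33 | 1 |
| Abnormal throughout | 180 | 1 |

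Shortening the gap by one minute moves the score from 10 to 1, with 3 more minutes abnormal.

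**2. Expected count with random deviations.** Assumptions, none from the documents: independent onsets at rate r per minute, each lasting D = 3 minutes, over T = 180 minutes. An onset is new if no other onset fell in the preceding a = 15 + D = 18 minutes. Then

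E(count) = 1 − exp(−ra) + r(T − a)exp(−ra)

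fraction of time out of range ≈ 1 − exp(−rD)

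- 1/h: ra = 0.3. Count = 0.259 + 2.7 × 0.741 = 2.26. Time out = 1 − exp(−0.05) = 4.9%.
- 2/h: ra = 0.6. Count = 0.451 + 5.4 × 0.549 = 3.41. Time out = 1 − exp(−0.1) = 9.5%.
- 4/h: ra = 1.2. Count = 0.699 + 10.8 × 0.301 = 3.95. Time out = 1 − exp(−0.2) = 18.1%.
- 8/h: ra = 2.4. Count = 0.909 + 21.6 × 0.0907 = 2.87. Time out = 1 − exp(−0.4) = 33.0%.

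Simulation with exponential durations of mean 3 minutes (4,000 patients per setting) gave 2.25, 3.41, 3.97 and 2.85, so the formula is adequate.

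Setting the derivative to zero gives a peak at r = T/[a(T − a)] = 180/(18 × 162) = 0.0617 per minute, or 3.7 per hour. The simpler approximation 60/(15 + D) gives 3.3 per hour here, and 3.75 to 2.4 per hour for mean durations of 1 to 10 minutes.

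**3. What this does to a comparison.** In each line NOL truly halves the onset rate (400 simulated trials, 72 per arm, which is the maximum of 144 split 1:1).

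| Routine vs NOL, onsets/h | Mean episodes | Result |
|---|---|---|
| 2 vs 1 | 3.42 vs 2.25 | right direction, significant in 100% |
| 4 vs 2 | 3.95 vs 3.41 | right direction, significant in 86% |
| 6 vs 3 | 3.52 vs 3.89 | NOL looks worse in 98.5% |
| 8 vs 4 | 2.87 vs 3.96 | NOL looks worse in 100% |

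Even where the direction is right, the effect shrinks. At 4/h vs 2/h the count ratio is 3.41/3.95 = 0.86, while the time-out-of-range ratio is 9.5/18.1 = 0.52.

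**4. If deviations cluster.** One stimulus may push several signs out together. With deviations in clusters of three within about 10 minutes (also an assumption), simulated mean counts at 1, 2, 4, 6, 8 and 12 deviations per hour were about 0.9, 1.6, 2.4, 2.8, 3.0 and 2.8. The 8/h vs 4/h comparison then has the right sign (3.0 vs 2.4), and the only fall is a slight one at 12/h. With clusters of two it is nearly flat (3.1 vs 3.0).

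**5. Case length.** At the same 2/h, the formula gives 0.451 + (102/30) × 0.549 = 2.32 episodes in 120 minutes and 0.451 + (222/30) × 0.549 = 4.51 in 240 minutes, with the same share of time out of range.

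**The case against.** Four points on the other side deserve weight.

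- A gap rule is a sensible guard against counting one event many times. The Background describes fentanyl as lasting typically about 15 minutes at first, so the 15-minute separation may have been chosen to match one bolus; that is an inference, as the plan gives no reason. This stands. The weakness lies in using the count alone.
- An unbroken deviation scores 1 under any episode count, so that example cannot be laid on the 15-minute rule. This also stands. What the rule adds is merging, across time and across criteria.
- A reader might infer that the comparison will point the wrong way, or that hypothesis 5 cannot be answered. The documents do not support that. They give no deviation rates or durations, the order is right at low rates, and clustering removes most of the reversal.
- A reader might infer that unequal case length biases the result. Under concealed 1:1 randomization it adds noise, not a systematic direction.

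It would also be wrong to assume that all the signals are stored every minute. The phrase "will also be recorded electronically at one-minute intervals" in Measurements has anesthetic drugs and details of surgery as its subject. Cuff pressure is every 3 minutes, and no interval is stated for heart rate or BIS.

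**Conclusion.** The point holds in a limited form. It follows from the wording alone that the count ignores duration and case length, pools opposite errors, and can score a patient who is out of range throughout below one who is out of range for 9 minutes. The non-monotone group mean rests on assumed independent 3-minute deviations in a 180-minute case, where the turn lies at about 3 to 4 onsets per hour. With both arms below that rate the count orders them correctly but understates the difference; with clustered deviations the fall is small or late. Reversal in this trial is therefore possible, not shown. The primary and secondary outcomes, the sample size and the interim boundaries are untouched. This is an inexpensive improvement to an exploratory outcome.

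**What to change.** Keep the episode count, but report it per hour of surgery. Add a co-reported hypothesis 5 outcome: the percentage of anesthesia time out of range, given separately for the inadequate component (systolic pressure, heart rate) and the excessive component (MAP, BIS), and adjusted for the stratification variable. Report diaphoresis, tearing and movement as any or none, since they have no recorded duration. State in advance that hypothesis 5 is supported only if the count and the time measure agree.

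The cost is wording in the aims and Data Analysis, with three details to settle:

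- a carry-forward rule between 3-minute cuff readings;
- confirmation of the recording interval for heart rate and BIS;
- one assignment of MAP below 65 mmHg, because Measurements lists it under inadequate analgesia while hypothesis 5 places it under excessive anesthesia.

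Requiring agreement is conservative: a real gain in time out of range would not count as support if the episode count went the other way. Both results should therefore be shown in full.
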